6.2 VTE DIAGNOSIS AND STUDY PROCEDURES

At all sites, VTE diagnosis will follow SOC procedures for diagnosis and treatment.

For patients suspected of VTE, this may include imaging only, or D-Dimer test followed by imaging or PTP score + D-Dimer testing + imaging. For all patients for whom VTE is not confirmed by imaging at the initial visit, the study will require that a 3-month follow-up is performed.

- Irrespective of the procedures used locally for VTE diagnosis, sites will be asked to evaluate patients with symptoms consistent with VTE (DVT and/or PE) using the Wells score without knowledge of D-Dimer and/or imaging results. The Wells score result may or may not be used for VTE diagnosis depending on sites' SOC.
- About 12 ml of venous blood will be taken from unlikely subjects (see definition on page 10) in order to obtain at least 6 aliquots of 1 mL of patient plasma each: plasma aliquots will then be banked frozen at -70°C
- STA® - Liatest® D-Di XL will later be used on banked frozen samples to assess assay's accuracy relative to the reference standard (imaging or 3-month follow-up). Only samples determined stable using the procedure described in Section 4.2 will be included in the study.
- Samples may also be used in future studies to evaluate new D-dimer test products to be used as improved diagnostic tools for DVT and/or PE (currently under development by Stago).

Plasma from patients with high Wells score will not be collected in the study.

6.3 WELLS SCORE

All testing sites will follow the same PTP model: the Wells score² (see Appendix A).

In case of patients showing symptoms of both DVT and PE, both Wells scores will be determined.

Patients suspect of DVT must have a Wells score for DVT ≤ 2 to be eligible in the study

Patients suspect of PE must have a Wells score for PE ≤ 6 to be eligible in the study

For those investigation centers where the Wells score is *not* part of routine practice the questions for the Wells score will be answered by the treating attending physician, and the score will be calculated without knowledge of the D-dimer test and imaging results. This process will be exactly consistent with what would be routine practice at the site.

6.4 D-DIMER TESTING WITH STA® - Liatest® D-Di XL

STA® - Liatest® D-Di XL D-Dimer testing will be performed at “testing sites” and staff performing the assay will be blinded to reference diagnosis.

6.4.1. Instruments

STA® - Liatest® D-Di XL test will be performed at testing sites (see sec. 2.1) on frozen banked samples using Stago instruments from Max® generation of the following families: STA-R® family , STA Compact® family or STA –Satellite® family (currently under development – will be included if available at the time testing with STA® - Liatest® D-Di XL begins).

The use of these instruments with STA® - Liatest® D-Di XL will require updated software version including :

- Modification in the homogenization process of reactional medium containing D-dimer plasma and anti-D-dimer antibodies
- Modification of the signal processing and calibration curve.

Software changes will be implemented only for the STA® - Liatest® D-Di XL test and they will not impact the instrument configuration used for other D-Dimer assays.

If one of the above mentioned Stago analyzer is already routinely used at the testing site, at the beginning of the testing phase a full check of the instruments, including application of the new

²Wells PS. Integrated strategies for the diagnosis of venous thromboembolism. *J Thromb Haemost*. 2007;5(Suppl. 1):41-50

Country-specific amendment for US sites

software version mentioned above, will be performed by Stago personnel. In addition, the performance of the instruments will be verified during site visits performed by Stago Technical personnel before study starts and will appear in the relevant validation report. The necessary quality control of the instruments should be performed by the laboratory personnel as per routine practice described in the instructions for use. This will be verified by the assigned monitor during monitoring visit.

The serial numbers and software versions will be recorded at the start of the study and included in the validation report.

If none of the above mentioned Stago analyzers are routinely used at the testing site, then at the beginning of the study Stago personnel will implement the Stago analyzer(s) at the site strictly following the process used by Stago to implement the analyzer in routine practice at clinical sites.

6.4.2. Reagents for STA® - Liatest® D-Di XL

The following reagents will be used in the study:

- STA® - Liatest® D-Di XL
- STA® - Owren-Koller (ref. 0360) / STA Diluent-Buffer (ref. 03138097)
- STA® - Cuvettes (ref. 38669)
- STA® - Cleaner Solution (ref. 0973) / STA Washing Solution (ref. 11447157)
- STA® - Mini Reducer (ref. 0797) / STA Reducer (ref. 11662996)
- STA® - Desorb U (ref. 0975) / STA Desorb U (ref. 11820192)
- STA® - D-Di Control
- STA® - D-Di Control Low.

6.4.3. VIDAS assay

VIDAS® D-Dimer Exclusion II™ (bioMérieux SA, RCS LYON 673 620 399, 69280 Marcy-l'Etoile / France, k112818) will be used to demonstrate sample stability (see sec. 4.2). As per package insert, the assay will be performed on instruments from the VIDAS family (VIDAS, miniVIDAS or VIDAS 3).

The package insert recommendations must be followed to perform D-dimer testing with VIDAS assay.

6.4.4. Collection and handling of patient samples

It is recommended to comply with CLSI Guideline H21-A5 Collection, Transport, and Processing of Blood Specimens for Testing Plasma-Based Coagulation Assays and Molecular Hemostasis Assays.

Blood samples will be collected at the initial visit using 3.2% trisodium citrate anticoagulant tubes, 1 volume of citrate for 9 volumes of blood. Plasma samples will then be centrifuged for 15 minutes at 2000-2500 g at room temperature. Alternative centrifugation conditions are allowed, provided that the

plasma is platelet poor (< 10000 platelets/mm³) or that the adopted centrifugation conditions were shown not to affect D-dimer results.

Plasma will be distributed in freezing tubes in at least 6 aliquots of minimum 1 mL. Plasma will then be frozen and stored at each site at a temperature below - 70 °C in a freezer that does not have defrosting cycles.

6.4.5. STA® - Liatest® D-Di XL testing (for testing sites only)

Before testing a sample with STA® - Liatest® D-Di XL the sample's stability must be established as described in Section 4.2. Briefly, each sample from “unlikely” subjects will have been tested with VIDAS assay either fresh or after freezing within 6 months of initial collection (see diagram on sec. 4.2). The same sample will be tested with VIDAS assay and with STA® - Liatest® D-Di XL within 4 hours from thawing. If the sample does not meet stability criteria described in sec. 4.2. (+/- 0.15 µg/mL for DDi levels below or equal to 1 µg/mL FEU at first testing; +/- 15% for DDi levels above 1 µg/mL FEU at first testing), it will be excluded from the study.

The package insert recommendations must be followed to perform D-dimer assays with the STA® – Liatest® D-Di XL. STA® – Liatest® D-Di XL is a pre-calibrated assay. The parameters of calibration are loaded in the analyzer with the bar-code printed on the bar-code insert.

Before testing, frozen plasma samples will be thawed in a water bath at 37°C for the needed time and mixed by reverse agitation before use.

D-dimer assay with STA® – Liatest® D-Di XL is performed using the instrument configuration set up by Stago (see 6.5.1). The assay will be run in singlicate.

STA® - D-Di Control and STA® - D-Di Control Low will be used to perform quality control for the STA® – Liatest® D-Di XL -dimer assay. Quality controls will be run according to instruction for use at least once a day or more if requested by local regulations.

D-dimer levels measured by STA® – Liatest® D-Di XL are expressed in fibrinogen equivalent units (FEU).

The STA® – Liatest® D-Di XL threshold is equal to 0.50 µg FEU/ml:

- the result is negative if sample level is inferior to 0.50 µg FEU/ml,
- the result is positive if sample level is superior or equal to 0.50 µg FEU/ml.

Testing of STA® - Liatest® D-Di XL will be performed at testing sites by site staff blinded to imaging or follow up results obtained at enrolling sites. A procedure will be set up before testing starts to ensure that blinding is rigorously maintained at each testing sites.

6.5 SAMPLE STABILITY AFTER FREEZING

As noted in Section 2.1, samples will be tested by VIDAS assay after freezing within 6 months of collection (6 months is a freezing time period not affecting sample stability as declared in the VIDAS package insert) and retested with the same assay at the time of testing with STA® - Liatest® D-Di XL.

Only samples meeting the acceptance criteria specified in Section 2.1 and for which associated QC results are in the QC ranges will be included in the primary efficacy analysis set (see sec. 9.4).

6.6 IMAGING STUDIES FOR VTE

Imaging techniques used for the study will include any technique used as a routine practice at the sites among which are: compression ultrasonography (CUS), ventilation/perfusion scan, helical computed tomography (CT) scan based on PIOPED II criteria, pulmonary angiogram and venography.

Technique(s) and equipment(s) used for imaging studies will be reported in medical records.

All imaging analyses and/or medical reports for each patient for the categories of patient for whom these data will be collected (see diagram in previous pages) will be archived.

6.7 FOLLOW UP

Patients for whom VTE was excluded as per SOC will be followed for 3 months to evaluate potential development of DVT and/or PE.

This follow-up will be performed by the clinician, the study coordinator or the nurse to obtain information regarding development of DVT and/or PE in the 3 months (i.e. 90 days) following Visit 1. The follow-up will have an allowed window of 1 month. Therefore it will take place in the period between 3 and 4 months (i.e. 90 to 120 days) after patient's first visit. The follow-up may be done using several methods according to site choice:

- Phone call to the patient,
- Medical record review if at enrollment patient states he/she does all its medical consultation at the investigation site and if he/she agrees that follow-up will be done by review of its medical record,
- Email to the patient asking the patient to call one site study representative if patient has given its consent to be contacted via email and server for email is secure,
- Call to family doctor in case patient is not answering the call.

The three-months follow-up information may be recorded directly in the CRF, in this case the CRF is considered as Source Document.

In addition, for female patients pregnant at the time of the follow up contact, all efforts will be done to determine if patient had an undetected pregnancy at visit 1, in which case the patient will be excluded from the study due to violation of an exclusion criterion.

If a patient cannot be contacted to collect follow-up information even beyond the 120 days from visit 1, he/she will be considered "lost to follow-up". But before declaring that a patient is "lost to follow-up", the PI (or his/her team) must do his/her best effort to contact patients and attempts should be made via all available routes, and when necessary, patients should be traced through relatives and examination of State death records. A certified letter should be sent to the permanent address on file. The methods used to attempt to contact the patient should be noted.

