5. STUDY POPULATION

5.1 INCLUSION / EXCLUSION CRITERIA

INCLUSION CRITERIA

1. Patient is < 80 years old.
2. Patient presents at least one of these symptoms indicative of proximal DVT or PE:
 - symptoms for **proximal DVT**: leg pain, tenderness (discomfort through palpation), leg swelling, and /or edema,
 - symptoms for **PE**: hemoptysis, lung related chest pain, dyspnea.
3. Patient provides written informed consent to participate in the study
4. Patient is willing to comply with specified follow-up evaluation at 3 months and can be contacted by telephone

EXCLUSION CRITERIA

1. Patient presenting with a condition that may be associated with increased D-dimer levels, even in the absence of VTE, such as:
 - Fibrinolytic therapy within the previous seven (7) days,
 - Disseminated intravascular coagulation
 - Bone fracture or surgery (with general anesthesia longer than thirty (30) minutes) within the previous one (1) month,
 - Deep hematoma diagnosed by imaging techniques within the previous one (1) month,
 - Disseminated malignancies and active cancer (active cancer defined as: cancer for which therapeutic or palliative treatment is either ongoing at the time of enrolment or has stopped less than six (6) months before enrolment),
 - Sepsis, severe infections, pneumonia within the previous 1 month,
 - Known liver cirrhosis,
 - Pregnancy or having delivered within the previous 1 month,
 - Atherosclerotic vascular disease thrombosis within the previous 1 month (e.g. myocardial infarction, stroke, coronary syndrome, peripheral artery disease stage III or IV),
 - Sickle cell disease,
2. Patients presenting with a suspect thrombotic event related to catheter implantation
3. Ongoing therapeutic anticoagulants (curative and preventive regimen) started twenty four (24) hours or more before blood draw (except aspirin and platelet inhibitors)
4. Previous anticoagulant therapy stopped less than three (3) months before blood draw (except aspirin and platelet inhibitors)
5. Patients with previous DVT/PE occurred less than three (3) months from screening.
6. Suspect thrombotic events in other locations at screening, including distal to the knee and upper extremity DVT (based on standard of care examinations)
7. Patients with known tissue plasminogen activator (tPA) deficiency
8. Patient participating or who has participated within one month of enrolment in another investigational study

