9.2 DESIGN CONSIDERATIONS

This is a prospective, multi-center study which will recruit consecutive subjects suspected of VTE. The population of interest includes those subjects classified “unlikely” by the Wells score system as specified in the CLSI guideline.

Following are central elements of this trial's design:

Separate Statistical Testing of DVT and PE: Logistically this trial will be conducted as a single study. However data obtained will be analyzed separately for DVT and PE subjects. Trial design is identical for both indications and statistical analyses are almost identical.

Blinding of follow-up data: All "unlikely" subjects excluded at Visit 1 by SOC D-dimer negative or by negative imaging will be followed for occurrence of VTE for up to three months. To minimize possible bias during follow-up:

- Testing of STA® - Liatest® D-Di XL will be performed by testing site staff blinded to imaging or follow up results. A procedure will be set up before testing starts to ensure that blinding is rigorously maintained at testing sites
- Stago will be exposed to recruitment rates and count of reference-positive cases for the purpose of blind sample size re-estimation. Company will be blinded to all other data (including, of course, device outcome). A standard operating procedure (SOP) will be developed to ensure that this in fact is the case.
- Company and designated statisticians will be blind to efficacy data throughout the trial. The electronic data capture (EDC) provider will create a file accessible to data management and statistics that includes all study data excluding Device result (level of D-dimer) and Device diagnosis (positive or negative). This will enable counting reference-positive cases blind to outcome, which is needed for blind sample size re-estimation. The provider will create a separate file that is accessible to the provider only, in which subjects' D-dimer results are entered. Files will be merged at data lock, after the final SAPs have been completed and signed. The procedure will be drawn up in an SOP.

STA® - Liatest® D-Di XL testing for the purpose of this trial will be done on banked samples collected from subjects at Visit 1.

Special efforts will be made by PI (or his/her team) to obtain follow-up clinical outcome for subjects who could not initially be reached by the standard follow-up procedures. Such efforts may include attempts to trace subjects through relatives and examination of State death records.

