9.3 ENDPOINTS

Primary Efficacy

For each "unlikely" subject, VTE diagnosed dichotomously (positive/negative) by:

- Reference Standard, which includes data obtained by imaging or follow-up,
- Device

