9.4 ANALYSIS SETS

The Primary efficacy analysis set will consist of all "unlikely" VTE subjects for whom there are valid observed values on both STA® - Liatest D-Di XL and Reference Standard (imaging or follow up). This includes "unlikely" subjects suspected of PE, or DVT or both; the latter will be included in both of the separate PE and DVT analysis sets. "Unlikely" D-dimer negative subjects having imaging result at Visit 1 will have imaging as reference. Device result is considered valid if it is not missing, its associated QC results are in the QC ranges and is deemed stable after thawing according to criteria provided in Section 4.2. Subjects with major protocol deviations likely to affect outcome will be excluded by blind review³. In line with CLSI guidelines, distal DVT subjects are not included in the primary efficacy analysis set for the DVT indication.

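### Chart review alone can supply the 3-month reference with no evidence standard, so a device-negative VTE treated elsewhere may be scored as a true negative and raise sensitivity

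*Combined protocol and SAP*

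**What the plan says.** Section 6.7 requires follow-up of patients in whom VTE was excluded under standard of care (SOC), and says that "it will take place in the period between 3 and 4 months (i.e. 90 to 120 days) after patient's first visit". On method, "The follow-up may be done using several methods according to site choice". Four options are listed: a phone call, chart review, an email asking the patient to call, and a call to the family doctor.

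The chart option reads "Medical record review if at enrollment patient states he/she does all its medical consultation at the investigation site", with a second condition that the patient agrees to be followed this way. The family-doctor call is reserved for patients who do not answer. Chart review has no such place in a sequence and can stand alone.

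Loss to follow-up is defined by failed contact: "If a patient cannot be contacted to collect follow-up information even beyond the 120 days from visit 1". The tracing steps (relatives, death records, certified letter) belong to that branch.

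Section 9.3 defines the endpoint through the "Reference Standard, which includes data obtained by imaging or follow-up". Section 9.4 admits subjects with "valid observed values on both STA® - Liatest D-Di XL and Reference Standard (imaging or follow up"). It then says what makes a device result valid (present, quality control in range, sample stable) but not what makes a follow-up result valid. It also says that D-dimer-negative subjects imaged at Visit 1 take imaging as their reference.

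Inclusion criterion 4 in section 5.1 is "Patient is willing to comply with specified follow-up evaluation at 3 months and can be contacted by telephone". Section 9.6 describes no analysis by follow-up method.

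**The concern.** For an "unlikely" subject cleared on SOC D-dimer and never imaged, follow-up is the only reference. The events it has to find are VTEs already missed by one D-dimer test, which makes them natural candidates for false negatives on the new assay. A statement at enrolment about where a patient consults cannot cover an unplanned visit to another emergency department, an event while travelling, or a death outside hospital.

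A site that reviews only its own chart may therefore see nothing and record no VTE. Because nobody tried to contact the patient, the tracing steps are not clearly triggered. If the subject did have a VTE and D-Di XL was negative, the case is counted as a true negative. Sensitivity drives the sample size and rests on few false negatives, so it is the endpoint exposed. Since the method is chosen by site, any shortfall in ascertainment may also differ between sites.

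**Working it through.** **Inputs.** From sections 9.5 and 9.6: 115 reference positives; assumed sensitivity 98%; two-sided 95% exact binomial limits; sensitivity needs a lower confidence limit (LCL) of at least 0.90 and a point estimate of at least 0.95; NPV needs an LCL of at least 0.95 and a point estimate of at least 0.97. Expected enrolment is 2,908 for PE and 1,870 for DVT. The share of subjects followed by chart alone and the rate of care elsewhere are not given.

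**1. The plan's own figure.** With n = 115, 110/115 = 0.957 has LCL 0.901 and passes; 109/115 = 0.948 has LCL 0.890 and fails. At most 5 false negatives (FN) are allowed. Exact power at 98% sensitivity is P(FN ≤ 5) = 97.1%, so the stated power of at least 90% is reproduced as a lower bound. Expected FN = 115 × 0.02 = 2.3.

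**2. Direction.** Sensitivity = TP/(TP+FN); NPV = TN/(TN+FN).
- Hidden VTE, device negative: moves from FN to TN. Both estimates rise.
- Hidden VTE, device positive: recorded as a false positive. NPV is unchanged and sensitivity is slightly understated. With 113/115 observed and 5 such cases, 0.9826 is reported where 118/120 = 0.9833 is true.

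**3. Tipping point for sensitivity.** Let f be the observed FN among 115 observed positives and k the hidden FN. Restoring them gives (115 − f)/(115 + k). The smallest k that turns a pass into a fail is:

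| f observed | Observed | Last k that passes | First k that fails |
|---|---|---|---|
| 2 | 113/115 = 0.983 | k = 3: 113/118, LCL 0.904 | k = 4: 113/119 = 0.9496, LCL 0.893 |
| 3 | 112/115 = 0.974 | k = 2: 112/117, LCL 0.903 | k = 3: 112/118 = 0.949, LCL 0.893 |
| 4 | 111/115 = 0.965 | k = 1: 111/116, LCL 0.902 | k = 2: 111/117 = 0.949, LCL 0.892 |
| 5 | 110/115 = 0.957 | k = 0: LCL 0.901 | k = 1: 110/116 = 0.948, LCL 0.891 |

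**4. Effect on error control, over an assumed range.** If a fraction h of FN is hidden, the sensitivity seen is s/(s + (1 − s)(1 − h)). At true s = 0.90 with 115 observed positives, the chance of passing is 2.2% for h = 0, 4.4% for h = 10%, 11.6% for h = 25% and 43.3% for h = 50%. The values of h are illustrative; the plan gives none.

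**5. NPV.** Specificity is not in the plan, so 40% to 75% is assumed. With 2 observed FN, TN is taken as (N − 115) × specificity, and k hidden cases give NPV = (TN − k)/(TN + 2). The least favourable case is DVT at 40%: TN = 702. With k = 10, NPV = 692/704 = 0.983, LCL 0.970, a pass. With k = 20, NPV = 682/704 = 0.969, just below the 0.97 point-estimate goal, although its LCL of 0.953 is still adequate. PE at 40% with k = 20 gives 1,097/1,119 = 0.980, LCL 0.970, a pass.

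**The case against.** Several stronger readings are tempting, and the documents do not support them.

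- A reader might infer that the plan scores a silent chart as negative. No sentence says so. Section 6.7 asks for information on VTE and section 9.4 asks for valid observed values; how an empty chart is classified is left open. What stands is a missing definition that each site must fill for itself.
- A reader might treat the patient's statement as the only safeguard. There are two conditions, and the statement must cover all consultations. Together they lower the risk of unseen outside care without removing it.
- A reader might say the error always favours the device. It does so only when D-Di XL is also negative. SOC D-dimer and D-Di XL are separate tests, so agreement cannot be assumed. Nor does the gap reach D-dimer-negative subjects imaged at Visit 1.
- A reader might stress that one hidden event can turn 109/115 (LCL 0.890, fail) into 109/114 (LCL 0.9006, pass). The arithmetic is right, but six FN among 115 has a probability of about 2% at the assumed 98% sensitivity, and one case at the boundary flips any exact test.

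It can also be said that section 9.6 already tests a site-by-reference interaction, and that the separate SAPs promised in section 9.1 may add analyses. The interaction test will have little power with so few FN and does not look at follow-up method. The SAPs remain the right place to close the gap.

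**Conclusion.** The point holds as a gap in the definition of the reference standard. Chart review without contact can supply the 3-month result, no minimum evidence is required for a negative, and the tracing steps do not clearly apply. The exposure lies mainly with unimaged subjects cleared on SOC D-dimer, and it favours the assay when D-Di XL is also negative.

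The size of the bias cannot be computed. What can be stated is how many hidden FN would reverse a sensitivity pass at 115 observed positives: from 1 (with 5 observed) to 4 (with 2 observed, close to the 2.3 expected). NPV is robust: under the assumed specificities and 2 observed FN, 10 hidden cases leave both goals met. A claim that both co-primary endpoints are equally at risk would go too far. This is a worthwhile, inexpensive improvement; the documents do not show that the trial's result is unreliable.

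**What to change.** **DVT subjects still to be followed.** Amend section 6.7 to require direct contact first (phone, or an email that leads to a call). Allow chart review or the family doctor as a supplement, or after documented failed contact. State that a chart with no entry on or after day 90 is not a negative reference and that the subject goes to the existing lost-to-follow-up steps. Record the follow-up method in the e-CRF.

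**PE and DVT subjects already followed by chart alone.** Report their number by device result. Before data lock, prespecify a tipping-point analysis in each SAP: how many device-negative chart-only subjects would have to move from true negative to false negative before a sensitivity or NPV goal fails, set against the number of such subjects. Simply excluding them is not enough. They are all reference-negative, so dropping them leaves TP/(TP+FN) unchanged and can alter only NPV.

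**Cost.** One call per affected subject, which criterion 4 already makes feasible; one e-CRF field; one table per indication. Slightly more subjects may be classed as lost to follow-up. PE data collection is complete, so only the reporting and tipping-point parts apply there.
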